7.4. Lost to Follow-up

Participants who cannot be contacted during the in-clinic evaluation period through Day 64 or at the Month 13 safety follow-up phone call and who do not have a known reason for study withdrawal (eg, withdrew consent or AE) will be classified as “lost to follow-up” as the reason for study withdrawal in the eCRF. The site will make three attempts to contact the participant by telephone, with contact attempts spaced at least one week apart. In the event the site is unable to reach the participant by telephone, the site will attempt to contact the participant via certified mail or an alternative similar method where appropriate.

Refer to [Section 8.1.8](#) for procedures when participants cannot be contacted at the Months 4, 7, and 10 safety follow-up phone calls.

8. STUDY ASSESSMENTS AND PROCEDURES

8.1. Schedule of Assessments

Individual participation in this study from the first visit to last visit inclusive of safety follow-up phone contacts will be approximately 15 months. Screening will be approximately one month (Day -28 to Day -2) followed by four in-clinic visits occurring over 2 months (9 weeks). Safety follow-up phone calls will be conducted at Day 43 and Months 4, 7, 10 and 13. The following sections also provide detailed lists of assessments to be performed by visit.

Of note, collection of the blood sample for immunogenicity assessments on vaccination days must be completed before the vaccine is administered.

A Schedule of Assessments is provided in [Table 6](#), in which visit windows are specified (eg, ± 1 day, meaning one day before or after the target visit day will be allowed).

A licensed physician will be identified as the PI for the site. The PI will designate appropriately qualified staff members to perform study tasks and procedures, including preparation and administration of the IP. Assessments of AEs and eligibility criteria may only be made by those with the medical training and authority to make a diagnosis. All task delegates will be recorded in the Delegation of Authority Log maintained at the investigational site.

Note: all study procedures/assessments outlined in Section 8.1 below will be performed by blinded member(s) of site staff, except where noted otherwise [eg, unblinded member(s) of site staff will prepare and administer the IP].

Table 6: Schedule of Assessments

Study Periods	Screening	In-clinic Visits					Safety Follow-up Phone Calls	Unscheduled Visit	Comments
		1	15 (±1)	29 (±2)	64 (±3)	EWV			
Study Day (Visit Window in Days)	-28 to -2	1	15 (±1)	29 (±2)	64 (±3)	EWV	43 (±2), 120 (±14), 211 (±14), 302 (±14), 394 (±14)	-	On unscheduled visit days: X _{<D64} = assessment to be performed only if before Day 64.
Sign and date ICF	X								-
Subject ID assigned	X								-
Demographics	X								-
Medical history	X	X							Any current signs and symptoms assessed as trial-procedure-related will be recorded as AEs, otherwise recorded as medical history.
Vital signs: systolic and diastolic blood pressure (sitting), heart rate, respiratory rate, and temperature	X	X	X	X	X	X		X _{<D64}	On vaccination days, vital signs will be taken before vaccination and at 30 minutes (± 5 min) postvaccination.
Vital signs: height and weight	X								-
Medication usage	X	X	X	X	X	X	X	X	Medications taken within 30 days prior to the Screening visit or since the last visit (including unscheduled visit) through Day 64/EWV will be recorded. Additionally, medication use will be recorded at the time of the safety follow-up phone calls (also during unscheduled visits following safety phone calls) only for those subjects who report an AE, SAE or AESI.

Study Periods	Screening	In-clinic Visits					Safety Follow-up Phone Calls	Unscheduled Visit	Comments
		1	15 (±1)	29 (±2)	64 (±3)	EWV			
Study Day (Visit Window in Days)	-28 to -2						43 (±2), 120 (±14), 211 (±14), 302 (±14), 394 (±14)	-	On unscheduled visit days: X _{<D64} = assessment to be performed only if before Day 64.
Complete PE	X				X	X			Abnormal findings are to be recorded as AEs after Day 1 postvaccination if new or increased in severity unless the PE abnormality is part of a symptom complex that is already reported as an AE.
Viral serology testing	X								Testing for HIV-1 or HIV-2 antibodies, hepatitis B surface antigen, and hepatitis C antibody.
Use of adequate method of contraception (WOCBP only)	X	X	X	X	X	X	X	X	The preferred method of adequate contraception as defined in Section 5.2 will be documented in the WOCBP's chart and reviewed for continued use at every visit or contact thereafter.
FSH	X								Performed to confirm postmenopausal status only in women having >12 consecutive months without menses.
Hematology	X			X		X			Any Grade 3 neutropenia or lymphopenia will be evaluated with an unscheduled repeat CBC approximately 72 hours after the initial specimen was drawn, unless a protocol-scheduled CBC has already shown resolution to Grade 1 or lesser toxicity. EWV will include hematology testing only if the visit occurs before Day 29.
Serum chemistry	X			X		X			EWV will include serum chemistry testing only if the visit occurs before Day 29.

Study Periods	Screening	In-clinic Visits					Safety Follow-up Phone Calls	Unscheduled Visit	Comments
		1	15 (±1)	29 (±2)	64 (±3)	EWV			
Study Day (Visit Window in Days)	-28 to -2						43 (±2), 120 (±14), 211 (±14), 302 (±14), 394 (±14)	-	On unscheduled visit days: X<D64 = assessment to be performed only if before Day 64.
Urinalysis	X			X		X			EWV will include urinalysis testing only if the visit occurs before Day 29.
Urine drug screening	X								Participants with any positive test result may not be randomized.
Pregnancy test: serum	X				X	X			Performed for all WOCBP including, at Screening only, women suspected to be postmenopausal. Exempt from pregnancy testing: women confirmed to be surgically sterile and confirmed to be postmenopausal after the Screening FSH test result is known. If the urine pregnancy test is positive, serum testing will be performed. Urine pregnancy test results will be captured in the eCRF.
Pregnancy test: urine		X	X	X					
Study eligibility	X	X							-
Continuing eligibility for vaccination			X	X					If a participant has any condition that, in the opinion of the PI or designee, would render vaccination unsafe for the participant (eg, febrile illness, pregnancy) or would interfere with evaluations, then the vaccination will be rescheduled (if the condition is likely to resolve and the rescheduled vaccination visit will still occur within the visit window) or discontinued.

Study Periods	Screening	In-clinic Visits					Safety Follow-up Phone Calls	Unscheduled Visit	Comments
		1	15 (±1)	29 (±2)	64 (±3)	EWV			
Study Day (Visit Window in Days)	-28 to -2						43 (±2), 120 (±14), 211 (±14), 302 (±14), 394 (±14)	-	On unscheduled visit days: X<D64 = assessment to be performed only if before Day 64.
Symptom-directed PE		X	X	X				X<D64	Symptom-directed PEs are to be conducted prior to vaccination on vaccination days. Abnormal findings are to be recorded as AEs after Day 1 postvaccination if new or increased in severity unless the PE abnormality is part of a symptom complex that is already reported as an AE.
Immunogenicity (TNA) testing		X		X	X	X			Blood for determination of TNA will be collected from participants before vaccination on days when injections are scheduled. A sample will be collected at the EWV only if within the visit window for Day 64.
Auto-antibody testing and thyroid-stimulating hormone (TSH) assessment		X			X	X		X	Blood samples will be collected for testing of RF, ANA and anti-dsDNA antibodies and TSH. The Day 1 samples are collected predose. A blood sample for auto-antibody testing will be collected at an unscheduled visit from participants reporting a potential AESI. A sample for TSH assessment will be collected at unscheduled visit(s) as per the investigator's discretion (ie, report of potential AESI).
Randomization of eligible participants		X							-

Study Periods	Screening	In-clinic Visits					Safety Follow-up Phone Calls	Unscheduled Visit	Comments
		1	15 (±1)	29 (±2)	64 (±3)	EWV			
Study Day (Visit Window in Days)	-28 to -2						43 (±2), 120 (±14), 211 (±14), 302 (±14), 394 (±14)	-	On unscheduled visit days: X _{<D64} = assessment to be performed only if before Day 64.
Vaccination		X	X	X					IP will be prepared by an unblinded member of site staff on Day 1. Participants will be vaccinated (by an unblinded member of site staff) as assigned by randomization on Day 1, followed by 30-minute observation (by a blinded member of site staff) for adverse effects of vaccination especially anaphylaxis.
Provision and instructions on use of the following: hand-held device, oral thermometer and injection site reaction measurement tool		X							A hand-held device will be provided only to those participants who do not have or do not wish to use their own personal device. Instructions on use of hand-held device, oral thermometer and injection site reaction measurement tool will be provided on Day 1 post-vaccination.
Participant e-diary entry		X→	→X→	X→					E-diary completion instructions and training will be provided on Day 1. Subjects will be instructed to complete the e-diary starting on the evening of Day 1 (with Day 1 being the day of first vaccination) and on every subsequent evening (for at least seven days). Participants are to complete the e-diary daily for at least seven days following each vaccination. If a reaction is not resolved at seven days postvaccination, the participant is to continue completing the e-diary daily until they are symptom free for two consecutive days.

Study Periods	Screening	In-clinic Visits					Safety Follow-up Phone Calls	Unscheduled Visit	Comments
		1	15 (±1)	29 (±2)	64 (±3)	EWV			
Study Day (Visit Window in Days)	-28 to -2						43 (±2), 120 (±14), 211 (±14), 302 (±14), 394 (±14)	-	On unscheduled visit days: X _{<D64} = assessment to be performed only if before Day 64.
E-diary review by PI/site staff			→X	→X→		X	X (Day 43 only)	X _{<D64}	Site staff will assess e-diary data daily and review it with participants at the Day 15 and 29 visits, as well as at unscheduled visits occurring before Day 64 and EWV if applicable. On Day 43 (±2 days), site staff will follow-up with a telephone call to review e-diary data entered by the participant after Day 29.
Collect hand-held device					X	X			The hand-held device will be collected from any applicable participants who did not already return it using the provided return packaging.
AEs	X	X	X	X	X	X	X	X	AEs will be followed until resolution, stabilization, or referral. From the signing of the ICF at the Screening visit until the first vaccination on Day 1, signs or symptoms resulting from trial-related procedures only will be recorded as AEs on the AE eCRF; all others reported in this time period will be recorded on the Medical History eCRF.
SAEs/potential AESIs		X	X	X	X	X	X	X	A list of AESIs is provided in Appendix B .

AE = adverse event; AESI = adverse event of special interest, eg, AE potentially associated with autoimmune disease as defined by CBER and might represent a safety signal for vaccine-associated autoimmunity; ALT = alanine aminotransferase; BUN = blood urea nitrogen; ANA = antinuclear antibody; AST = aspartate aminotransferase; CBC = complete blood cell count; dsDNA = double-stranded deoxyribonucleic acid; EWV = early withdrawal visit; FSH = follicle-stimulating hormone; HBV = hepatitis B virus; HCV = hepatitis C virus; HIV = human immunodeficiency virus; ICF = informed consent form; ID = identification; NA = not applicable; PE = physical examination; RBC = red blood cell; RF = rheumatoid factor; SAE = serious adverse event; TNA = toxin neutralizing antibody; WBC = white blood cell; WOCBP = women of childbearing potential

EWV procedures are to be performed for participants who withdraw from the study before Day 64.

Safety follow-up phone calls occur at Day 43, Months 4, 7, 10, and 13 (nominally 0.5, 3, 6, 9, and 12 months after the last vaccination).

8.1.1. Screening (Days -28 to -2)

Participants will be screened for participation in the trial from 2 to 28 days prior to the Day 1 (randomization) visit. The screening period starts once the ICF is signed and dated. The following activities will occur during the Screening visit or period:

- Ensure review and completion of all required information on the ICF and capture in site source documentation
- Assign the subject ID number
- Record demographics
- Record medical history including current signs and symptoms, which will be recorded as AEs only if they result from a study-related procedure(s)
- (For WOCBP only) document in the participant's chart about counsel received for the requirements around type and timing of an adequate method of contraception, including the participant's preferred method
- Conduct complete PE
- Assess vital signs and height and weight
- Record medications taken within the last 30 days
- Collect blood sample for:
 - Viral serology (human immunodeficiency virus [HIV] antibodies, hepatitis B surface antigen [HBsAg], and hepatitis C antibody)
 - FSH (performed to confirm postmenopausal status only in women having >12 consecutive months without menses)
 - Hematology
 - Serum chemistry
 - Serum pregnancy test (women only, exempting women who are documented to be surgically sterile; refer to [Section 5.1](#))
- Collect urine sample for:
 - Urinalysis
 - Urine drug screening
- Review for study eligibility against inclusion/exclusion criteria, to include a review of all safety and screening laboratory results (based on the central laboratory's reference ranges, or if outside the ranges, based on the investigator's assessment of clinical significance) once available

8.1.2. Day 1 (Randomization, Day of First Vaccination)

The following will occur on Day 1 prior to vaccination:

- Update medical history including signs and symptoms, which will be recorded as AEs only if the event results from a study-related procedure
- Assess vital signs
- Conduct symptom-directed PE
- Record medications taken since the last visit
- Collect blood samples for:
 - TNA testing
 - RF, ANA and anti-dsDNA antibodies testing
 - TSH assessment
- Confirm continued use of an adequate method of contraception and collect urine sample for pregnancy test for WOCBP (if positive, the participant must not be randomized; upon receipt of a negative confirmatory serum pregnant test result, the participant may be rescheduled for the Day 1 visit providing the visit falls within the required window of the screening procedures [refer to [Section 5.4](#)])
- Review for study eligibility against inclusion/exclusion criteria, to include a review of all safety and screening laboratory test results (based on the central laboratory's reference ranges, or if outside the ranges, based on the investigator's assessment of clinical significance) and status of ongoing AEs since the prior visit
- Randomize eligible participants

The participant will be vaccinated (by an unblinded member of site staff) as per the randomization group assignment.

The following will occur after vaccination [as performed by blinded member(s) of site staff]:

- Monitor participants for at least 30 minutes postvaccination for adverse effects of vaccination, especially anaphylaxis
- Assess vital signs at 30 ± 5 minutes postvaccination
- Provide hand-held device to those participants requiring one to access the web-enabled e-diary, eg, participant does not have or does not wish to use own personal device; pre-paid return packaging will be provided with the device, to enable the participant to mail the device at the conclusion of all e-diary entries
- Instruct participant on use of the e-diary/provided hand-held device
 - E-diary is to be completed starting on the evening of Day 1 (the day of first vaccination) and on every subsequent evening (for at least seven days). Participants are to complete the e-diary daily for at least seven days following each vaccination. If a reaction is not resolved at seven days postvaccination, the participant is to continue completing the e-diary daily until they are symptom free for two consecutive days.

- Provide an oral thermometer and injection site reaction measuring tool and instruct the participant on their use
- Assess the participant for AEs, SAEs, and AESIs

8.1.3. Day 15 ± 1 day (Day of Second Vaccination)

The following will occur on Day 15 ± 1 day prior to vaccination:

- Assess vital signs
- Record medications taken since the last visit
- Confirm continued use of an adequate method of contraception and collect urine sample for pregnancy test for WOCBP (if positive, a confirmatory serum pregnancy test is required)
- Conduct symptom-directed PE
- Assess the participant for AEs, SAEs, and AESIs, including review the status of ongoing AEs since the prior visit
- Review e-diary entries with the participant
- Review eligibility for continuing vaccination (refer to [Section 6.1.2](#))

The participant will be vaccinated (by an unblinded member of site staff) as per randomization group assignment.

The following will occur after vaccination [as performed by blinded member(s) of site staff]:

- Monitor participants for at least 30 minutes postvaccination for adverse effects of vaccination, especially anaphylaxis)
- Assess vital signs at 30 ± 5 minutes postvaccination
- Assess the participant for AEs, SAEs, and AESIs

8.1.4. Day 29 ± 2 days (Day of Third Vaccination)

The following assessments will occur prior to vaccination:

- Assess vital signs
- Conduct symptom-directed PE
- Collect blood samples for:
 - TNA testing
 - Hematology
 - Serum chemistry
- Collect urine samples for:
 - Urinalysis

- Urine pregnancy test for WOCBP (if positive, a confirmatory serum pregnancy test is required); also confirm continued use of an adequate method of contraception
- Record medications taken since the last visit
- Review e-diary entries with the participant
- Assess for AEs, SAEs, and AESIs, including review the status of ongoing AEs since the prior visit
- Review eligibility for continued vaccination (refer to [Section 6.1.2](#))

The participant will be vaccinated (by an unblinded member of site staff) as per the randomization group assignment.

The following will occur after vaccination [as performed by blinded member(s) of site staff]:

- Monitor participants for at least 30 minutes postvaccination for adverse effects of vaccination, especially anaphylaxis)
- Assess vital signs at 30 ± 5 minutes postvaccination
- Assess for AEs, SAEs, and AESIs

8.1.5. Day 43 \pm 2 days (Safety Follow-up Phone Call)

The following assessments will be performed over the phone:

- Review of e-diary and any ongoing AEs/SAEs/AESIs (if applicable)
- For WOCBP, confirm continued use of an adequate method of contraception and inquire about any possible pregnancies (refer to [Section 9.3](#))
- Record medications taken since the last visit or contact

8.1.6. Day 64 \pm 3 days (Final In-clinic Visit)

The following assessments will be performed on the Day 64 \pm 3 days in-clinic visit:

- Assess vital signs
- Record medications taken since the last visit
- Perform complete PE
- Collect blood sample for:
 - TNA testing
 - RF, ANA and anti-dsDNA antibodies testing
 - TSH assessment
 - Serum pregnancy test for WOCBP; also confirm continued use of an adequate method of contraception

- Assess for AEs, SAEs, and AESIs, including review the status of ongoing AEs since the prior visit
- Collect the hand-held device used for the e-diary (if applicable), if not already returned

8.1.7. Early Withdrawal Visit

Early withdrawal visit procedures will be performed for participants receiving at least one vaccination who withdraw from the study before Day 64. The following will occur during the EWV:

- Perform complete PE
- Assess vital signs
- Collect blood samples for laboratory testing:
 - Hematology (only if the EWV occurs before Day 29)
 - Serum chemistry (only if the EWV occurs before Day 29)
 - Serum pregnancy testing for WOCBP; also confirm continued use of an adequate method of contraception
 - TNA testing (only if the sample collection is within the visit window for Day 64)
 - RF, ANA and anti-dsDNA antibodies testing
 - TSH assessment
- Collect urine sample for urinalysis (only if the EWV occurs before Day 29)
- Record medications taken since the last visit
- Assess e-diary data since the last visit, if applicable
- Assess for AEs, SAEs, and AESIs, and verify the status of ongoing, previously-reported AEs to determine if resolved
- Collect the hand-held device used for the e-diary (if applicable), if not already returned

8.1.8. Safety Follow-up Phone Calls at Month 4 ± 14 Days, Month 7 ± 14 Days, Month 10 ± 14 Days, and Month 13 ± 14 Days

All due attempts will be made to follow participants who receive at least one vaccination for safety through Month 13 (nominally 12 months after the last vaccination, presuming full compliance with the vaccination schedule), particularly for late onset autoimmune events. To mitigate loss to follow up within the year-long period, participants will be contacted by site staff at quarterly intervals. These phone contacts will be scheduled keying off the subject's actual or, if missed, target Day 29 visit (intended last vaccination day), so that all participants (even those failing to receive all three vaccinations but who are followed for safety only) are contacted at Month 4 (Day 120 ± 14 days; nominally 3 months after Day 29 final vaccination), Month 7 (Day

211 ± 14 days; nominally 6 months after Day 29 final vaccination), Month 10 (Day 302 ± 14 days; nominally 9 months after the Day 29 final vaccination), and Month 13 (Day 394 ± 14 days; nominally 12 months after the Day 29 final vaccination).

The following assessments will be performed over the phone at the Month 4, Month 7, Month 10, and Month 13 contacts:

- Assess and document AEs, SAEs and potential AESIs (refer to [Section 9.3](#))
- For WOCBP, confirm continued use of an adequate method of contraception and inquire about any possible pregnancies (refer to [Section 9.3](#))
- Record medications taken since the last visit or contact (if related to AE, SAE and/or AESI)
- Review the status of ongoing AEs/SAEs/AESIs to update the resolution status

During the telephone calls, the staff member is to inquire about and record in source documentation any AEs and SAEs occurring since either the Day 64 visit or the preceding phone contact. Any occurrence of SAE will be reported to Emergent immediately as specified under [Section 9.3](#) and followed up per procedures described in [Section 9.6.2](#). If an SAE has occurred, it will be recorded on the AE eCRF with any medications taken also recorded on eCRFs.

During the telephone calls, the staff member will also attempt to elicit and record in source documentation any information on AESIs of potential autoimmune etiology. If the condition is a diagnosed or suspected AESI, the staff member may refer the participant to the PI or designee for further phone evaluation if needed; based on initial assessment of potential AESI, the participant will be asked to return for an unscheduled clinic visit for evaluation (refer to [Section 8.1.8](#)) and to provide a blood sample for auto-antibody testing and/or TSH assessment (if applicable). The PI or designee will obtain records confirming the diagnosis or refer the participant to a medical specialist for additional clinical and diagnostic testing and follow up until the diagnosis is ascertained. The potential AESI will be reported to Emergent immediately as specified in [Section 9.3](#) and followed up per procedures described in [Section 9.6.2](#). Only after the DSMB has assessed the case as a confirmed AESI will the PI or designee record the occurrence of the AESI on the AE eCRF with any medications taken also recorded on eCRFs. The MM or designee will direct the completion of the AE eCRF when communicating the DSMB assessment outcome(s) to the PI or designee.

In the event the site is unable to reach the participant by telephone at any of the interim safety follow-up calls at Day 43, Months 4, 7, or 10, at least three phone contact attempts must be made before the site documents that the participant was unable to be reached. The contact attempts will be spaced at least one week apart. Failure to reach the participant at one of the interim safety follow-up time points does not preclude contact attempts at the next scheduled safety follow-up time point. Procedures for the final Month 13 call are described in [Section 7.4](#).

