3.2.2. Secondary Endpoints

The secondary study endpoints are as follows:

Immunogenicity:

- Lower bound of the two-sided 95% CI will be ≥ 67% for the proportion of AV7909 participants in Groups 1-3 (three lots pooled) achieving a TNA NF₅₀ ≥ 0.15 on Day 29.

Safety:

- Incidences of AEs from the time of the first vaccination on Day 1 through Day 64
- Incidences of clinical laboratory abnormalities
- Incidences of autoimmune-associated AESIs from the time of the first vaccination on Day 1 through the 12-month safety follow-up telephone call following the last vaccination
- Incidences of solicited systemic reactions and solicited injection site reactions by severity following each vaccination as reported in participant e-diaries

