Pregnancy testing will be performed at all visits including EWV. Female participants who are confirmed at Screening to be surgically sterile (refer to [Section 5.1](#)) are exempt from pregnancy testing. A serum pregnancy test is required at Screening for all other female participants, including those suspected to be postmenopausal; any such individuals who are confirmed to be postmenopausal after the Screening FSH test result is known (refer to [Section 5.1](#)) are exempted from further pregnancy testing. Postscreening pregnancy testing in WOCBP (only) will consist of a urine pregnancy test at all visits except for a serum pregnancy test performed at Day 64 and the (if applicable) EWV. All urine pregnancy tests must be performed at the investigational site and documented to be negative on vaccination days before administration of vaccine. For participants with positive urine test results, a confirmatory serum pregnancy test will be performed. Vaccination will not be administered to any participant who tests positive for pregnancy.

Blood and urine samples for safety clinical laboratory testing (hematology, serum chemistry, urinalysis) will be collected at Screening and Day 29 and also at the EWV if the EWV occurs before Day 29. Refer to [Table 7](#) for the complete list of analytes to be tested. Blood samples for auto-antibody assessment of RF, ANA and anti-dsDNA antibodies and TSH will be taken at Day 1 prior to vaccination, Day 64/EWV, and at the time of unscheduled visit(s) if warranted from participant report(s) of potential AESI(s) at the safety follow-up phone call(s).

Clinical laboratory results for the lab analytes that appear in [Table 9](#) will be assigned by the central laboratory a toxicity grade (Grade 1=mild through Grade 4=potentially life-threatening)

according to the FDA Guidance for Industry: *Toxicity Grading Scale for Healthy Adult and Adolescent Volunteers Enrolled in Preventive Vaccine Clinical Trials* {[CBER, 2007](#)}. This grading – assessing severity – will aid the PI or designee in the evaluation of laboratory abnormalities and their reporting, if applicable, as AEs.

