2.2.3.2 Clinical Laboratory Assessments

All analytes to be tested during screening/safety clinical laboratory tests are specified in [Protocol EBS.AVA.212, Table 7](#).

The following assessments will be performed at Screening only:

- Urine drug screen (refer to Protocol EBS.AVA.212, Table 7 for analytes)
- Serologic testing (HIV-1/HIV-2 antibodies, HBV surface antigen, and HCV antibody). Confirmatory testing will be performed on any samples that test positive for either HIV or HCV; no additional blood/serum will be required for this confirmatory testing.
- FSH test to confirm postmenopausal status in women having > 12 consecutive months without menses (refer to [Protocol EBS.AVA.212, Section 5.1](#)).

Pregnancy testing will be performed at all visits including EWV. Female participants who are confirmed at Screening to be surgically sterile (refer to Protocol EBS.AVA.212, Section 5.1) are exempt from pregnancy testing. Vaccine will not be administered to any subject who tests positive for pregnancy.

Blood and urine samples for safety clinical laboratory testing (hematology, serum chemistry, urinalysis) will be collected at Screening and Day 29 as well as at the EWV if the EWV occurs before Day 29. Refer to Protocol EBS.AVA.212, Table 7 for the complete list of analytes to be tested. Blood samples for auto-antibody assessment of RF, ANA and anti-dsDNA antibodies and TSH will be taken at Day 1 prior to vaccination, Day 64/EWV, and at the time of unscheduled visit(s) if warranted from participant report(s) of potential AESI(s) at the safety follow-up phone call(s).

All samples will be sent to the central laboratory for analysis, except urine for pregnancy testing in women of childbearing potential (WOCBP), which will be performed at the site and results documented in the eCRF.

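### The early-withdrawal safety panels depend on the date of the visit, not on whether the Day 29 samples were taken, so some withdrawing participants have no scheduled post-vaccination hematology, chemistry or urinalysis

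*Protocol*

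**What the plan says.** Four places set the same rule.

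- Protocol 8.1.7 (Early Withdrawal Visit) has three bullets: "Hematology (only if the EWV occurs before Day 29"), "Serum chemistry (only if the EWV occurs before Day 29") and "Collect urine sample for urinalysis (only if the EWV occurs before Day 29").
- Protocol Table 6 (Schedule of Assessments) repeats the rule in its comments on each panel, for example "EWV will include hematology testing only if the visit occurs before Day 29".
- Protocol 8.3.2 says that safety blood and urine samples "will be collected at Screening and Day 29 and also at the EWV if the EWV occurs before Day 29".
- SAP 2.2.3.2 says that they "will be collected at Screening and Day 29 as well as at the EWV if the EWV occurs before Day 29".

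An EWV applies to anyone who has had at least one vaccination and withdraws before Day 64. The Day 64 visit (Protocol 8.1.6) includes none of the three panels. Protocol 3.2.2 lists "Incidences of clinical laboratory abnormalities" as a secondary safety endpoint.

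SAP 3.3, Table 3 assigns Days 27 to 31 to the Day 29 analysis visit. SAP 7.3 tabulates the highest post-baseline toxicity grade without naming a denominator. The default in SAP Appendix I is all participants in the analysis population. Only by-visit summaries are limited to those present at the visit.

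**The concern.** The date condition works only if everyone seen on or after Day 29 has already given the Day 29 samples. The protocol itself does not assume this: Protocol 8.1.8 schedules the follow-up calls from the target Day 29 date when that visit was missed.

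A person who misses the draw and then attends an EWV sits in the clinic, gives blood for other tests, and leaves without the panels that inform the laboratory endpoint. With a single scheduled post-vaccination time point, no later scheduled sample replaces it. Under the default denominator, that person then enters the highest-grade table as someone without an abnormality, when in fact nothing was measured.

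**Working it through.** The point turns on the text, so the first step is to apply the rule by day of the EWV, for a vaccinated participant with no Day 29 sample.

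| EWV day | Panels under the written rule | SAP Table 3 analysis visit |
|---|---|---|
| 27–28 | drawn | Day 29 (27–31) |
| 29–31 | not drawn, read literally | Day 29 (27–31) |
| 32–60 | not drawn | none |
| 61–63 | not drawn | Day 64 (61–67) |

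The second row shows the misfit most clearly: a sample that would count as a Day 29 result is not taken. The TNA condition in the same EWV list is tied to a visit window (that of Day 64), whereas the safety-panel condition uses a bare day.

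**What is still collected.** Every EWV takes RF, ANA, anti-dsDNA and TSH, and serum pregnancy for women of childbearing potential, with no Day 29 condition. The gap is confined to hematology, chemistry and urinalysis.

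**Size.** The documents do not say how many participants would miss Day 29 and then have an EWV, so no count can be derived. For scale, take the plan's own detection statement (Protocol 10.1), which reproduces:

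P(at least one event) = 1 − (1 − 0.001)^3000 = 95.03%, against a stated 95%.

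Now assume that a fraction m of the 3000 AV7909 participants has no post-vaccination panel. These values of m are assumptions, not estimates.

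| m | Untested | Tested | 1 − 0.999^n, n = tested |
|---|---|---|---|
| 1% | 30 | 2970 | 94.9% |
| 2% | 60 | 2940 | 94.7% |
| 5% | 150 | 2850 | 94.2% |
| 10% | 300 | 2700 | 93.3% |

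Even 10% untested costs under two percentage points (95.0 − 93.3 = 1.7).

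**Denominator.** If untested people stay in the denominator, then

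reported percentage = (1 − m) × percentage among those tested.

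The factor is 0.99, 0.98, 0.95 or 0.90 for the four values of m. Here m covers everyone without a post-baseline panel, whatever the reason. The ratio between arms is multiplied by (1 − m_AV7909)/(1 − m_BioThrax), which is 1 when the two fractions are equal. Nothing in the documents says that they would differ.

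**The case against.** The strongest reply is that the affected group is narrow and partly covered.

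- **Stopping vaccination is not missing Day 29.** Protocol 6.1.2 and 7.3.1 keep vaccinated participants in the safety visits. Those followed for safety only are excused from TNA draws and vaccination-linked assessments, not from the Day 29 panels. This stands and narrows the group to people who miss the draw and then come for an EWV.
- **For-cause testing exists.** Unscheduled visits (Protocol 8.1.9) and additional tests (8.3.2) are available. Both respond to an adverse event or an abnormal result, so they do not reliably replace a missed routine sample.
- **The condition could mean before the Day 29 visit.** That reading would rescue Days 29 to 31, but no passage states it, and it would not help after Day 31. The ambiguity is itself a reason to reword.
- **Late samples say less.** In EBS.AVA.201, differences between groups in lymphocyte and neutrophil counts were not notable by Day 7, so a Day 40 sample would add little on such transient changes. This stands as a limit on what the extra draws can show.
- **The SAP already puts unscheduled data in maximum-grade summaries** (SAP 3.3). This helps, but an EWV is a separate visit type in Table 6, so one explicit sentence is still worthwhile.

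A reader might infer that these participants have no post-vaccination laboratory data at all. The auto-antibody and TSH draws at every EWV contradict that. A reader might also size the problem from the 5 of 44 (11.4%) who stopped product for an adverse event in Arm 1 of EBS.AVA.208. That is a rate of stopping product; the protocol does not say that those people withdrew or lacked samples.

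**Conclusion.** The gap is real and the same in all four places: it is an omission applied consistently, not a contradiction. A participant who misses the Day 29 draw and has an EWV on Days 29 to 63 has no scheduled post-vaccination hematology, chemistry or urinalysis for a secondary safety endpoint. For Days 29 to 31 this rests on reading Day 29 as a calendar day.

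The consequence is modest. The number is unknown and probably small, the loss in rare-event detection is negligible, and the laboratory analyses are descriptive. Counting untested people as free of abnormality is a separate and avoidable error in the highest-grade table, unless the table shells already override the default denominator.

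A reader might conclude that the laboratory profile will look cleaner, and more so in one arm. The documents do not support this. They do not show that those who leave early have more abnormalities, the listed withdrawal reasons include loss to follow-up and withdrawn consent, and no difference between arms is given. A reader might also want a catch-up panel at Day 64. The sponsor scheduled no such panel there for anyone, and this point does not depend on adding one.

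**What to change.** In Protocol 8.1.7, Table 6 and 8.3.2, and in SAP 2.2.3.2, replace the date condition with one that requires the panels at the EWV if the Day 29 safety labs have not been obtained.

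In SAP 7.3:

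1. Include these EWV draws in the highest-grade post-baseline table. Draws after Day 31 should stay out of the by-visit tables; otherwise Table 3 would place a draw on Days 61 to 63 under Day 64.
2. Base that table's percentages on participants with at least one post-baseline result for the analyte.
3. Report, by arm, how many vaccinated participants have no post-baseline panel.

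The burden is one extra tube and a urine sample for a few participants at a visit that already draws blood. Some of these samples will lie further from the last dose than Day 29. The text changes are small: three bullets in 8.1.7, three comments in Table 6, and one sentence each in 8.3.2 and SAP 2.2.3.2. The protocol part needs an amendment under Protocol Section 14.

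The SAP's handling of duplicate enrollments (4.9.2 and Appendix IV) shows that enrollment and vaccination had begun when it was written. If the in-clinic visits are already over, the collection change comes too late, but items 2 and 3 still apply and need no new data.
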